3.4.1.2. ASSESSMENT PERIOD

During the daily PE period, assessments should be performed at approximately the same time with frequency as detailed in the Schedule of Assessments.

⁺⁺⁺ Note that study drug administration can occur on Day 2 as a time window of 24 hours is permitted between the start of first PE (i.e., PE administered prior to randomization) and the start of the first PE after randomization (i.e., the first on-study PE), resulting in a possible time window between randomization and first study drug administration.

After the end of daily PE, subjects will return for ambulatory visits planned once weekly. All weekly visits should occur at the indicated week \pm 1 day.

Of note, as tapering of PE after platelet count normalization is strongly discouraged, visits in the 30-day post-daily PE period are linked to end of daily PE (not taking into account possible tapering).

All assessments will be performed as specified in the [Schedules of Assessments](#).

Unscheduled visits may be planned to assess, confirm, and follow up on clinically relevant AEs or laboratory abnormalities. Findings made during these unscheduled visits should be reported in the designated sections of the eCRF.

Missed visits:

All attempts should be made to follow the original visit schedule. If a subject misses a visit, he/she should come to the site as soon as possible after the planned missed visit.

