3.2 Determination of sample size

The primary hypothesis of interest in this study is to test the superiority of caplacizumab compared to placebo with respect to the time to platelet count response (initial platelet count $\geq 150 \times 10^9/L$ with subsequent stop of daily PE within 5 days). The required sample size is

calculated to obtain a power of at least 80% to detect a significant reduction in time to platelet count response using a two-sided Log-rank test, at a significance level of 5%. The accrual period is taken to be 2.5 years and the time-to-event period is set at 45 days. An estimated reduction of time to platelet count response for subjects in the caplacizumab arm of 40% is assumed. With a median time to response in the placebo arm assumed to be 7 days, this would correspond with a median time to response in the caplacizumab arm of 4.2 days. In addition, an expected drop-out rate of 10% in the first 10 days after first administration of study drug is taken into account in the calculations. Based on these assumptions a total sample size of 132 subjects (121 events) will provide a power of 80%.

A total sample size of 132 subjects will also provide approximately 83% power to detect a 20% reduction in the first key secondary endpoint, using a two-sided chi-squared test with a large sample approximation and a 5% significance level. This assumes incidence rates of 30% and 10% in the placebo and caplacizumab arms, respectively.

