4) No platelet count $\geq 150 \times 10^9/L$ and at day x subject early terminated with no initial platelet count response ($x \leq 45d$)	No	1	x	
5) Platelet count $\geq 150 \times 10^9/L$ (at day x) after being below $150 \times 10^9/L$, with subject early terminated within 5 days while on dPE	Yes	0	x	
6) Stop of dPE at day x without platelet count $\geq 150 \times 10^9/L$ ($x \leq 45d$)	No	1	x	
7) Stop of dPE at day x without platelet count $\geq 150 \times 10^9/L$ and platelet count $\geq 150 \times 10^9/L$ at day x+y ($x \leq 45d$, $y > 0d$)	No	1	x	

8) Platelet count $\geq 150 \times 10^9/L$ at day x with stop of dPE 5+y days later ($y > 0$), platelet count stays $\geq 150 \times 10^9/L$ as of day x ($x+y \leq 45$ days)	Yes	0	x+y	
9) Platelet count $\geq 150 \times 10^9/L$ at day x with stop of dPE 5+y days later ($y > 0$), platelet count has not been $\geq 150 \times 10^9/L$ between day x+y and day x+y+5 ($x+y+5 \leq 45$ days)	No	1	x+y+5	
10) Study drug withdrawn at day x with no Platelet count $\geq 150 \times 10^9/L$, and the subject early terminated y days later ($y > 0$, $x+y \leq 45$ days). The subject was still on dPE until early termination	No	1	x	

Time to platelet count response in the caplacizumab arm and placebo arm will be compared by conducting a two-sided stratified Log-rank test based on a Kaplan-Meier (KM) analysis, with severity of neurological involvement (according to the GCS, stratification factor used in randomization: $\leq 12 / 13-15$) as stratification factor. The resulting p-value will be compared with the significance level α of 5%. In case the p-value is smaller than 0.05 and the estimated median time to platelet count response in the caplacizumab treatment group is smaller than in the placebo treatment group, a significant reduction of time to platelet count response by caplacizumab will be concluded and the primary endpoint will have been met.

This analysis will be performed on the ITT population. Subjects will be analyzed according to the treatment to which they were assigned. Switch of subjects who experience a recurrence of TTP during the study to open-label caplacizumab will not affect the primary efficacy endpoint analysis as a recurrence can only occur after platelet count response, i.e. initial platelet count $\geq 150 \times 10^9/L$ with subsequent stop of daily PE within 5 days, has been reached.

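### The primary success rule takes its direction from the Kaplan-Meier medians, not from the stratified log-rank statistic that supplies the p-value

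*SAP*

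**What the plan says.** SAP 6.1.1 tests the primary endpoint with a two-sided log-rank test stratified by GCS category. It then sets two joint conditions for success: p below 0.05, and that "the estimated median time to platelet count response in the caplacizumab treatment group is smaller than in the placebo treatment group". Only when both hold is a reduction concluded and the endpoint counted as met. A Cox hazard ratio with its confidence interval is reported but has no part in the decision.

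The rule leaves three things open:

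- It does not say which median is meant. Medians are tabulated by GCS category and overall.
- It does not say what follows if the medians are equal or cannot be estimated. Because the comparison is strict, a tie fails.
- It does not say what follows if the medians and the test point in opposite directions.

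Protocol 3.6.4.1 specifies the two-sided stratified log-rank test at 5% and no condition on medians. SAP 12.1, which lists changes from the protocol made before database lock, does not mention the added condition.

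SAP 6.2.1 lets the key secondary tests proceed when the null hypotheses ranked above them, including the primary, have been rejected. It does not refer to the medians.

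**The concern.** A two-sided test needs a direction rule, and the natural one is the sign of the statistic tested. The log-rank statistic sums over the whole curve, whereas the estimated median is one point on each curve with its own sampling error. The two can disagree in either direction:

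- A significant test favouring caplacizumab is not called a success, because its median is equal or slightly longer.
- A significant test favouring placebo is called a success, because the caplacizumab curve is ahead at the median and behind later.

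Platelet counts are scheduled once a day, and Protocol 3.4.1.2 asks that "During the daily PE period, assessments should be performed at approximately the same time". Close or tied medians are therefore conceivable. What is at stake is the primary claim and, depending on how SAP 6.2.1 is read, access to the key secondary tests.

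**Working it through.** **The plan's own figure.** Inputs are from SAP 3.2: a test "using a two-sided Log-rank test, at a significance level of 5"%; a placebo median of 7 days, from which the SAP derives that "this would correspond with a median time to response in the caplacizumab arm of 4.2 days"; and, for losses, "an expected drop-out rate of 10% in the first 10 days after first administration of study drug". The same section adds: "The accrual period is taken to be 2.5 years and the time-to-event period is set at 45 days".

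- Ratio of medians: 4.2/7 = 0.6. With exponential times this is the hazard ratio (1.67 when expressed as a ratio for response).
- Schoenfeld events: 4(1.960 + 0.842)² / (ln 0.6)² = 31.4/0.261 = 120.3, so 121.
- Power at 121 events: Φ(√121 × 0.511/2 − 1.960) = Φ(0.85) = 80.2%.
- Drop-out hazard: −ln(0.9)/10 = 0.0105 per day. Event hazards: ln 2/7 = 0.0990 and ln 2/4.2 = 0.1650 per day.
- P(event by Day 45) = λ/(λ+δ) × [1 − exp(−45(λ+δ))] = 0.897 for placebo and 0.940 for caplacizumab, mean 0.918. Then 132 × 0.9185 = 121.2 events.

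This matches the SAP's statement that "a total sample size of 132 subjects (121 events) will provide a power of 80"%. The calculation concerns the log-rank test alone; the median condition is not in it.

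**The two criteria can disagree.** Take 66 subjects per arm, all with events and times to two decimals. Caplacizumab: 34 times evenly spaced from 1 to 4.10 days and 32 from 4.15 to 7. Placebo: 34 from 1 to 4.00 and 32 from 4.50 to 30. The medians are 4.01 days (caplacizumab) and 3.91 days (placebo). The unstratified log-rank z is 4.13 in favour of caplacizumab (p = 0.00004), with a hazard ratio for response of 2.36 (95% CI 1.55 to 3.58). The SAP rule is not met.

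**How often.** Simulated trials had 66 per arm, exponential or piecewise-exponential times, a placebo median of 7 days, drop-out as above and censoring at Day 45. The log-rank test was stratified, with 8% of subjects assumed to have GCS ≤12 (the documents give no figure). Two-decimal times were either continuous or from once-daily sampling on each subject's own clock. Entries are percentages of all trials.

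| Scenario | Time scale | Test favours caplacizumab, its median not smaller | Test favours placebo, caplacizumab median smaller |
|---|---|---|---|
| Planned effect (4.2 v 7) | two decimals | 0.1 to 0.4 | 0 |
| Planned effect | whole days | about 1, nearly all ties | 0 |
| Late separation: equal to Day 5, then response hazard × 2.5 | two decimals | 4 to 5 | 0 |
| Late separation | whole days | 11 to 12, mostly ties | 0 |
| Crossing: response hazard × 1.3 to Day 6, then × 0.3 | two decimals | 0 | 14 to 15 |

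The crossing result depends on drop-out. It is 14 to 15% if the drop-out hazard continues to Day 45, and about 19 to 20% if drop-out stops at Day 10. With no treatment effect, the rule is met in 2.5 to 3.0% of trials (Monte Carlo error about 0.2 points), so there is no sign of an inflated false-positive rate.

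**Which time scale applies.** SAP 6.1.1 measures from each subject's own loading dose and reports days to two decimals, so the two-decimal rows apply. One route leads to whole days: a missing sample time is set to the first dosing time minus 1 minute, and the formula adds 1 minute, which gives an exact whole number of days. The documents do not say how often sample times will be missing. The whole-day rows are therefore an upper bound.

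**The case against.** The best defence is that the rule is pre-specified and coherent. Protocol and SAP both state the planned effect as a shorter median, so asking the median to agree before claiming a shorter time is reasonable. The hazard ratio sits in the same table, so a disagreement would be visible. At the planned effect disagreement is very rare. Phase II showed a hazard ratio of 2.2 with a clearly lower median, and nothing in the documents predicts late separation or crossing. All of this stands as a limit on the size of the problem. It does not explain why direction should come from a different statistic than the p-value.

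Three stronger readings are tempting, and the documents do not support them.

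- *The rule costs a meaningful amount of power.* Figures of 1.1% at the planning medians, or 2.4% at the Phase II medians (3.0 and 4.8 days), arise only if times are rounded up to whole days. The SAP uses two decimals on a dose-anchored clock. The Phase II medians also belong to a different endpoint, confirmed platelet count normalization (Protocol 1.2.4).
- *The median condition gates the whole hierarchy.* SAP 6.2.1 speaks of rejected null hypotheses and of tests that are not significant, which is the language of the p-value. Whether a significant test with tied or discordant medians opens the sequence is unclear; neither answer is stated.
- *Sampling at about the same time each day puts event times on a shared whole-day grid.* It does not, because each subject's clock starts at that subject's own loading dose.

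**Conclusion.** The concern holds as a flaw in the form of the decision rule, of minor weight. SAP 6.1.1 adds to the protocol's test a condition based on another statistic, without recording it as a change. Under proportional hazards at the planned effect, it costs about 0.1 to 0.4 points of power, or about 1 point at the whole-day upper bound. The sample size justification is not affected.

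The rule gives a wrong answer mainly when hazards are not proportional, a possibility that SAP 6.1.1 itself plans to check. The illustrative sizes are about 5 points of power with late separation, and about 14 to 15% of trials called a success against a significant unfavourable test with crossing curves. Both rest on assumed curve shapes, exponential pieces and an assumed drop-out pattern. They show what the rule permits, not what this trial should expect.

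The link to the key secondary sequence is an ambiguity to close, not a demonstrated error.

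**What to change.** In SAP 6.1.1, replace the median condition. Conclude a reduction when the two-sided stratified log-rank p-value is below 0.05 and the sign of the stratified log-rank statistic favours caplacizumab. A Cox hazard ratio for response above 1 is an acceptable alternative, provided it is stated as caplacizumab relative to placebo. Keep the medians and their confidence intervals as description.

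In SAP 6.2.1, state that the key secondary sequence opens on this same criterion. List the change in SAP 12.1, and make it before unblinding.

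The cost is a sentence or two. The 132 subjects, 121 events and 80% nominal power stay as they are, and the chance of a false claim of benefit is held at 2.5%, half of the two-sided 5%. No data collection or clinical procedure changes. This is a free improvement.

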3 STUDY DESIGN

3.1 Overall study design

This is a phase III, randomized, double-blind, placebo-controlled study to evaluate the efficacy and safety of caplacizumab treatment when administered in addition to standard of care treatment (daily PE + corticosteroids) in subjects with an acute episode of acquired TTP. The study will evaluate the efficacy of caplacizumab in more rapidly restoring normal platelet counts and the effect of treatment with caplacizumab on a composite endpoint of TTP-related mortality, prevention of recurrence of the presenting TTP episode and prevention of major thromboembolic events during study drug treatment.

[figure not shown]
After confirmation of eligibility to study participation and after the start of PE treatment, 132 adults will be randomized in a ratio of 1:1 to either receive caplacizumab or placebo in addition to standard of care therapy. Randomization will be stratified by severity of neurological involvement (Glasgow coma scale [GCS] ≤12 vs. GCS=13-15). Stratification is foreseen to ensure balanced treatment arms for the key secondary endpoints related to neurological involvement and not for the primary endpoint for which the stratification parameter is not known to be relevant.

In addition, in specific centers that approved inclusion of these subjects, the study is open for recruitment of children (aged ≥2 to <12 years) and adolescents (aged ≥12 to <18 years) with

acquired TTP, requiring treatment with PE. Potential enrollment of pediatric subjects will be stopped once the enrollment objective for adult subjects has been met.

After confirmation of eligibility to study participation and after the start of PE treatment, pediatric subjects will be allocated to open-label treatment with caplacizumab.

An overview of the study design is as follows (see also CSP Section 3.1.1 for more details):

Note: Randomization is not applicable for children and adolescents as they will be allocated to open-label treatment with caplacizumab.

The anticipated study duration per subject is approximately 2 months in case of no treatment extensions and no exacerbations, and up to approximately 6 months in case of treatment extension and exacerbation during the 30-days post-daily PE period or relapse during treatment extension. The end of the study is defined as the last visit of the last subject participating in the study.

The Schedule of Assessments can be found in [Appendix A: Schedule of Assessments](#).

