- Baseline organ damage marker categories (LDH, cTnI, serum creatinine): <=ULN / >ULN
- Baseline platelet count. This parameter is assessed by a local laboratory.
- Baseline SMMSE total score
- Baseline RICO activity, vWF:Ag concentration and FVIII:C activity
- Baseline complement factors C5a and C5b-9
- Severity of disease at baseline category: very severe / less severe. Very severe is defined as French severity score ≥ 3 **or** severe neurological involvement at baseline (i.e., coma, seizures, focal deficit) **or** cardiac involvement (cTnI $> 2.5 \times$ ULN). The French severity score (Benhamou, 2012) is a discrete score from 0 to 4, involving evaluation of three parameters: cerebral involvement: yes = 1 / no = 0, LDH: $>10 \times$ ULN = 1 / $\leq 10 \times$ ULN = 0, age: >60 years = 2 / >40 and ≤ 60 years = 1 / ≤ 40 years = 0.

A detailed list of tables and listings can be found in Section [14.1](#) and Section [16.1](#), respectively.

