Besides the p-value, the table on the primary analysis will include standard KM estimates such as the median, 25% percentile and 75% percentile of the time to platelet count response by treatment group with associated 95% CIs, as well as the number of events and the number of censored observations. This summary will be presented both by GCS category, and overall, i.e. unadjusted by GCS category.

The KM estimates will also be presented graphically, unadjusted by GCS category.

The data will also be analyzed using a Cox proportional hazards regression model with time to platelet count response as dependent variable, and treatment group and GCS category as independent variables. The hazard ratio (HR) from the Cox model will be reported along with 95% CI in the table. The adequacy of the Cox model will be tested using the graphical and numerical methods of Lin, Wei, and Ying (1993). The proportional hazards assumption will be checked by using a transform of the martingale residuals known as the empirical score process. The assumption will be tested graphically by plotting for each covariate the simulated score processes, representing score processes under the proportional hazards assumption, and comparing them to the observed score process. In addition, a supremum test will be reported to assess the proportion of simulated score processes that yielded a maximum score larger than the maximum observed score process. A very small proportion (p-value) suggests violation of proportional hazards. In case the proportional hazards assumption does not hold, effect of potential confounding factors such as use of rituximab, disease severity at baseline, and baseline ADAMTS13 activity levels will be explored using stratified proportional hazards model(s), if feasible (i.e. depending on number of subjects in strata).

The following sas code will be used as starting point for the primary analysis.

For the Kaplan-Meier (KM) analysis:

```
proc lifetest data=inputdata;
  time aval*cnsr(1);
  strata trt01p trt01pn / test=(logrank);
  ods output quartiles=quartile CensoredSummary=censor;
run;

where
INPUTDATA is the input dataset
AVAL is the time to the event variable,
CNRS is 0 (subjects with events) or 1 (subjects without no event,
i.e. subject censored)
TRT01P and TRT01PN are respectively the categorical and numeric
versions of the planned treatment groups used for the subjects during
the DB treatment period
```

For the stratified Log-rank test:

```

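### The Cox model behind the reported primary hazard ratio omits baseline platelet count, which is already collected and is the variable whose rise defines the event

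*SAP*

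**What the plan says.** The primary endpoint (SAP Sections 3.3.1 and 6.1.1) is the time to a platelet count of at least 150 x10^9/L followed by stop of daily plasma exchange within 5 days. Exclusion criterion 1 (protocol Section 3.2.2) keeps out only counts of 100 x10^9/L or more, so subjects may start anywhere below 100.

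The endpoint is decided by a log-rank test stratified by GCS category, together with the direction of the medians (SAP 6.1.1). A Cox model is also fitted, with "treatment group and GCS category as independent variables"; the SAS code in the same section has the same two terms. Its hazard ratio and 95% CI are printed in the primary-endpoint table (SAP Section 14.2.1).

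On GCS, SAP Section 3.1 says that stratification serves the neurological key secondary endpoints and "not for the primary endpoint for which the stratification parameter is not known to be relevant".

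SAP Section 5.3 lists among the baseline characteristics: "Baseline platelet count. This parameter is assessed by a local laboratory". The schedule of assessments has the count taken at screening and on Day 1 before dosing. It appears in no covariate list, stratum, sensitivity analysis or subgroup for the primary endpoint (SAP 6.1.1, 6.1.2, 6.3). If proportional hazards fails, the factors named for exploration are rituximab use, disease severity and ADAMTS13 activity. The severity category is built from age, LDH, neurological involvement and cTnI, not from platelets.

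**The concern.** The event is the crossing of a fixed threshold, and the starting value of the same variable differs between subjects. It is plausible that a subject who starts at 90 gets to 150 sooner than one who starts at 10. The plan uses this idea elsewhere: the refractory-TTP key secondary endpoint (SAP 6.2.1) divides the later count by the starting count.

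The hazard ratio in the primary table is the effect size that readers will take away. If starting count is prognostic and the arms differ on it by chance, the GCS-only hazard ratio carries that difference. The Cox inference also forgoes precision that a recorded covariate could supply. What is at stake is the quality of a supportive estimate, not the success criterion.

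**Working it through.** **Inputs from SAP Section 3.2.** Test: "count response using a two-sided Log-rank test, at a significance level of 5" per cent. Size: "a total sample size of 132 subjects (121 events) will provide a power of 80" per cent. Effect: "With a median time to response in the placebo arm assumed to be 7 days" and "a median time to response in the caplacizumab arm of 4.2 days". Loss: "an expected drop-out rate of 10% in the first 10 days after first administration of study drug". Event window 45 days; allocation 1:1, so 66 per arm.

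**1. The plan's own figure.** The ratio of medians is 4.2/7 = 0.6, or 7/4.2 = 1.667 as a response-rate hazard ratio.
- Schoenfeld events: 4(1.960 + 0.842)^2 / (ln 0.6)^2 = 120.3, rounded up to 121.
- Power with 121 events: (sqrt(121)/2) x 0.511 - 1.960 = 0.850, and Phi(0.850) = 80.2%.
- Drop-out hazard: -ln(0.9)/10 = 0.01054 per day. With exponential event times and censoring at 45 days, P(event) is 0.897 on placebo and 0.940 on caplacizumab. Expected events: 66 x (0.897 + 0.940) = 121.2.

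The stated 132 subjects, 121 events and 80% power are reproduced.

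**2. Assumption.** The documents do not say how strongly baseline count predicts response. Take a standardized baseline covariate with log hazard b per SD, for b = 0, 0.2, 0.3, 0.5, 0.7. The response-rate hazard ratio per SD is then 1.00, 1.22, 1.35, 1.65, 2.01.

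**3. Chance imbalance.** With 66 per arm, the standard error of the difference in covariate means is sqrt(2/66) = 0.174 SD. An imbalance of that size shifts the unadjusted hazard ratio by about exp(0.174b). This is a first-order approximation.

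| HR per SD | Shift factor |
|---|---|
| 1.22 | 1.04 |
| 1.35 | 1.05 |
| 1.65 | 1.09 |
| 2.01 | 1.13 |

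Applied to 1.667, this gives 1.73 to 1.88 if the imbalance favours caplacizumab, and 1.61 to 1.48 if it favours placebo.

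**4. Efficiency of the Cox Wald test.** Simulated trials had N = 132, the drop-out hazard above and 45-day censoring. The Cox model was fitted with and without the covariate. GCS was left out because the documents give neither its split nor its effect. The plan's 1.67 comes from arm medians, so it is read as marginal: the conditional effect was set so that unadjusted power stays near 80% (4,000 runs each).

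| HR per SD | Unadjusted HR | Adjusted HR | Unadjusted power | Adjusted power |
|---|---|---|---|---|
| 1.22 | 1.69 | 1.73 | 80% | 83% |
| 1.35 | 1.68 | 1.74 | 80% | 84% |
| 1.65 | 1.70 | 1.87 | 81% | 92% |
| 2.01 | 1.69 | 1.97 | 80% | 95% |

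With no prognostic effect and a hazard ratio of 1.667, both models have about 79% power (3,000 runs). With no treatment effect, both reject in 4.6% to 5.4% of runs (2,000 runs per setting).

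**5. Alternative reading.** If 1.667 is entered as the conditional hazard ratio, adjusted power is about 78% throughout. Unadjusted power is 76, 72, 65 and 57%, and the unadjusted hazard ratio is 1.65, 1.62, 1.56 and 1.50. The plan does not define 1.67 this way, so the table in step 4 is the fairer one.

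**The case against.** **The Cox model decides nothing.** This stands. Success rests on the stratified log-rank test. A reader might infer from step 4 or step 5 that the trial is underpowered or would gain power from the change. It would not: the power figures belong to a Wald test with no decision role.

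**The smaller unadjusted hazard ratio is not bias.** This also stands, and it rules out a second tempting inference. A hazard ratio averaged over baseline count and one conditional on it are different quantities, and the first lies nearer 1 whenever the covariate matters. Adding the covariate changes what is estimated. Over repeated randomizations the GCS-only model also rejects at about 5% under the null. The point about imbalance concerns the particular allocation the trial ends up with.

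**Prognostic strength is assumed.** Correct. Protocol Section 3.1.2 cites a retrospective review on the rate of platelet rise over the first days of plasma exchange, not on the starting level. Baseline is the last value before study drug (SAP 4.3.1), normally after one plasma exchange of unrestricted intensity, so it is not an untreated value. The endpoint also depends on when exchange stops. Any of these could weaken the association, which is why the range has to include no effect.

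**GCS belongs in the model.** Agreed. It is the randomization factor, and the SAP's remark that it is not known to be relevant to this endpoint is no ground for removing it.

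**Imbalance will be visible in the baseline table.** True, but seeing it does not correct the estimate. Adjusting after seeing it would be post hoc.

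**Conclusion.** The point holds as a limited one. The hazard ratio and interval in the primary table adjust only for a factor not known to matter for this endpoint. They ignore a recorded baseline value of the very variable that defines it. The cost is exposure of the supportive estimate to chance imbalance (a factor of about 1.04 to 1.13 per standard error) and lower efficiency of the Cox test (about 80% against 83-95%).

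Both ranges rest on an assumed 1.22 to 2.01 per SD, a log-linear effect, exponential times and the plan's drop-out rate. At no prognostic effect both costs vanish, and the extra term costs essentially nothing.

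The documents do not support the claim that the confirmatory analysis, type I error or sample size is at fault.

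**What to change.** Keep the GCS-stratified log-rank test as the confirmatory test and keep the planned GCS-only Cox model. Before database lock, add to SAP 6.1.1 a second Cox model on the ITT population with treatment, GCS category and log baseline platelet count (continuous, last value before first study drug). Print its hazard ratio and 95% CI beside the planned one, labelled as a conditional, covariate-adjusted estimate. Record the change in SAP Section 12.1.

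The definition of baseline gives no value for a subject who is randomized but never dosed, so name the screening value to use in that case.

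The cost is one extra term in a PHREG call, one extra result in the primary table and no new data. If unblinding has already taken place, the analysis can still be run but must be reported as post hoc.
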